# Study Protocol with Statistical Analysis Plan

## Scientific Background

Loss of the interdental papilla is a frequent aesthetic concern, particularly in the anterior region where even minor deficiencies create visible black triangles. These deficiencies contribute to plaque accumulation, food impaction, and phonetic disturbances, in addition to compromising smile harmony. Earlier attempts to reconstruct missing papillae through surgery often yielded unpredictable outcomes, largely due to the delicate blood supply of the papillary region. As a result, attention has shifted toward non-surgical injectable biomaterials designed to restore soft-tissue volume with minimal invasiveness.

Hyaluronic acid (HA) dermal fillers have become widely used in aesthetic and periodontal therapy due to their biocompatibility, hydrophilicity, and ability to stimulate wound healing. Clinical studies have consistently reported partial or complete closure of black triangles following repeated HA injections. Injectable platelet-rich fibrin (i-PRF), prepared via low-speed centrifugation, represents an autologous alternative that provides a fibrin scaffold enriched in platelets and leukocytes. Its gradual release of growth factors promotes angiogenesis, fibroblast proliferation, and extracellular matrix formation.

Despite increasing interest, direct comparisons between these two materials are scarce, and previous trials have not used a split-mouth design to minimize interpatient variability. This study directly compares HA and i-PRF administered under identical intraoral conditions. We hypothesized that both would yield significant improvement in papilla fill without clinically meaningful differences between them.

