## Study design

This randomized split-mouth clinical trial included 13 systemically healthy adults with a total of 65 papilla deficiencies in the aesthetic zone. The study was approved by the Altınbaş University Ethics Committee. All participants provided written informed consent.

Inclusion criteria required  $\geq 2$  papillae classified as Papilla Presence Index (PPI) class 2 or 3, probing depths  $\leq 3$  mm, and plaque and bleeding scores below 15%. Exclusion criteria included PPI class 4, diastema, active periodontal disease, smoking, pregnancy, systemic conditions influencing healing, anticoagulant use, and previous surgical papilla reconstruction.

For each participant, one side was randomly assigned HA and the contralateral side i-PRF. The clinical examiner underwent intra-examiner calibration until repeated measurements were consistent within  $\pm 1$  mm. Outcome assessments were performed by a blinded examiner.

For i-PRF sites, 10–20 mL of venous blood was collected into plastic tubes and centrifuged at 700 rpm for 3 minutes. The upper orange plasma layer was aspirated and transferred to 1-mL insulin syringes. Injections were delivered within 5 minutes to ensure liquid consistency before polymerization.

All treatments were performed with buccal infiltration anesthesia. HA or i-PRF (0.1–0.2 mL) was injected from the buccal aspect, 2–3 mm apical to the papilla tip, at a 45° angle. A single

puncture per session was used to minimize trauma. Slight blanching indicated correct placement. Each papilla received three injections at baseline, week 3, and week 6.

Participants avoided mechanical oral hygiene for 24 hours and interdental brushes for one week, replacing them with 0.12% chlorhexidine rinses. Modified Bass brushing resumed the following day.

Standardized photographs were obtained using a custom photograph standardization device (PSD), enabling consistent image acquisition. Black triangle height (BTH), width (BTW), area (BTA), and papilla height (PH) were measured at baseline, 1 month, and 3 months using ImageJ. PPI was recorded visually. Radiographs were taken to measure the distance between the interdental bone crest and contact point (IBC-ICP). Keratinized tissue thickness (KTT) was measured at baseline.

Pain was assessed after each injection using a VAS scale from 0 (none) to 10 (worst). Aesthetic satisfaction was rated at each visit using a VAS scale from 0 (not satisfied) to 10 (highly satisfied).

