## Statistical Analysis Plan

The data were analysed using the Statistical Package for the Social Sciences (SPSS) version 26.0. The normality of distribution for the numerical variables related to the patients and the evaluated interdental papilla sites was assessed based on skewness and kurtosis values. Normality of continuous data will be assessed using the Shapiro–Wilk test and visual inspection of Q–Q plots. A reference range of  $\pm 1.96$  was adopted as the criterion for normal distribution (Kalayci, 2005).

For each material, changes over time from baseline to follow-up will be analysed using repeated-measures ANOVA when assumptions are met, or the Friedman test in the case of non-parametric or ordinal data. Post-hoc pairwise comparisons between time points will include Bonferroni adjustments. Since the study design is split-mouth, inter-group comparisons between HA and i-PRF at each time point, as well as comparisons of change scores, will use paired t-tests for normally distributed variables and Wilcoxon signed-rank tests otherwise. PPI, being ordinal, will be evaluated with non-parametric paired procedures. Subgroup analyses will be performed separately for maxillary and mandibular papillae using similar paired or repeated-measures methods. Patient-reported VAS outcomes will be analysed using repeated-measures methods for within-group changes and paired testing for between-group differences.

Comparisons of KTT and IBC-ICP measurements across jaw localizations and treatment groups, as well as intergroup analyses of clinical outcome variables, were performed using the One-Way ANOVA test. Intragroup comparisons of variables measured at different time points were conducted using the Repeated Measures ANOVA. Where applicable, Post Hoc tests were employed to further investigate significant intergroup differences.

Additionally, to evaluate the relationship between KTT and IBC-ICP measurements and the percentage changes in clinical parameters, the Spearman correlation test was used. In interpreting the correlation coefficients, a range of 0.00–0.30 was considered low, 0.30–0.70 moderate, and 0.70–1.00 high. A significance level of  $p < 0.05$  and  $p < 0.01$  was adopted for all statistical analyses.

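### Testing HA against i-PRF separately in each jaw does not test whether the material difference depends on jaw, and no planned analysis does

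*Combined protocol and SAP*

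**What the plan says.** The subgroup plan is one sentence in the Statistical Analysis Plan: "Subgroup analyses will be performed separately for maxillary and mandibular papillae using similar paired or repeated-measures methods". The paired methods it refers to are those for HA versus i-PRF at each time point and on change scores, which "will use paired t-tests for normally distributed variables and Wilcoxon signed-rank tests otherwise".

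Jaw appears in one other place in that section, a One-Way ANOVA: "Comparisons of KTT and IBC-ICP measurements across jaw localizations and treatment groups". In that phrase, jaw is tied to keratinized tissue thickness and to the bone crest to contact point distance. Neither is among the photographic or PPI outcomes.

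Bonferroni adjustment is stated only for pairwise comparisons between time points. The significance level of 0.05 (and 0.01) "was adopted for all statistical analyses", with no provision for subgroups and no rule for reading them.

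Under Study design, the trial "included 13 systemically healthy adults with a total of 65 papilla deficiencies in the aesthetic zone", and "one side was randomly assigned HA and the contralateral side i-PRF". The numbers of maxillary and mandibular papillae are not given, nor is the number of participants contributing to both jaws.

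**The concern.** Two within-jaw p-values answer two questions: do the materials differ in the maxilla, and do they differ in the mandible? Neither asks whether the difference is larger in one jaw than in the other. When power within a jaw is moderate, the two tests will often disagree by chance although the effect is identical.

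At stake is a statement that the materials differ in one jaw but not the other, which would invite choosing a material by jaw. The planned analysis could produce that pattern but could not support the conclusion.

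**Working it through.** **Nothing to reproduce.** The documents contain no sample-size calculation, power, effect size or SD.

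**Inputs from the documents.** 13 participants and one material per side (Study design); paired t-test for HA versus i-PRF and a significance level of 0.05 (Statistical Analysis Plan).

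**Assumed inputs.** Two-sided testing; one HA minus i-PRF difference per patient per jaw; all 13 participants contribute to both jaws; the same true effect d in both jaws, in SD units of that difference; correlation rho between a patient's two jaw differences.

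**Step 1: power within one jaw.** This is p(d) = P(|T| > 2.179), where T is noncentral t with 12 degrees of freedom and noncentrality d√13.

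**Step 2: exactly one jaw significant, jaws uncorrelated.** The general form is p1(1 − p2) + p2(1 − p1). With equal powers it is 2p(1 − p):

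- d = 0: 2 × 0.050 × 0.950 = 0.095
- d = 0.2: 2 × 0.102 × 0.898 = 0.183
- d = 0.4: 2 × 0.264 × 0.736 = 0.389
- d = 0.6: 2 × 0.512 × 0.488 = 0.500
- d = 0.8: 2 × 0.754 × 0.246 = 0.371

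**Step 3: allow for the same patients in both jaws.** A patient's two jaw differences may well be correlated. Simulation (100,000 runs per correlation) gives the proportion of trials with exactly one jaw significant:

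| True effect | rho = 0 | rho = 0.3 | rho = 0.5 | rho = 0.7 |
|---|---|---|---|---|
| none | 10% | 9% | 8% | 7% |
| 0.2 SD | 18% | 16–17% | 15% | 12% |
| 0.4 SD | 39% | 33% | 28% | 22% |
| 0.6 SD | 50% | 42% | 35% | 27% |
| 0.8 SD | 37% | 31–32% | 27% | 21% |

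These rates are per outcome and visit. Four photographic outcomes "were measured at baseline, 1 month, and 3 months using ImageJ", giving 4 × 2 = 8 outcome-by-visit comparisons at follow-up, plus PPI. If the 8 were independent with no true difference, at least one one-jaw-only pattern would occur with probability 1 − (1 − 0.095)^8 = 0.55. That is an upper illustration, because the outcomes are correlated.

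**Step 4: the direct test.** Take each participant's maxillary difference minus the mandibular difference and apply a one-sample t-test. With equal effects it was significant in 4.9–5.1% of runs at every correlation. A two-sample test that treats the jaws as independent samples does not hold 5% when the same patients supply both. Its rate falls to about 2% at rho = 0.3 and 0.2% at rho = 0.7.

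**Step 5: change over time.** A large common change is detected in both jaws almost every time. At 1.5 SD, p = 0.9986, and 2 × 0.9986 × 0.0014 = 0.003. At 1.2 SD the rate is about 3–5%.

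**Step 6: power of the direct test.** In units of the within-jaw SD, the contrast has SD √(2(1 − rho)). If the material effects truly differ between jaws by 0.6 SD, the standardised contrast at rho = 0 is 0.6/√2 = 0.42, and power is 29%. At rho = 0.7 it is 0.6/√0.6 = 0.77, and power is 73%. Both assume all 13 contribute to both jaws.

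**The case against.** Several objections limit the point, and most of them stand.

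- **The rate depends on an effect the trial does not expect.** The Scientific Background hypothesises improvement with both materials "without clinically meaningful differences between them". With no difference, the one-jaw-only rate is 7–10% per comparison. A reader might infer that about half of all such trials would mislead. That holds only near 0.6 SD with uncorrelated jaw differences, and the documents establish neither.
- **Change over time.** The subgroup sentence also covers repeated-measures analyses, so a reader might extend the criticism to them. The Scientific Background expects significant improvement, and for a large change the misleading pattern nearly disappears (step 5).
- **The One-Way ANOVA.** A reader might infer that it was meant as a jaw-by-material test of the outcomes and is the wrong one. The phrase about jaw concerns two anatomical measurements, and the cells for the outcome ANOVA are not defined. All that follows is that it does not supply the missing contrast.
- **The 5% rate.** It cannot be claimed for every interaction test. It is shown for the within-participant contrast, fails for a two-sample test, and has not been checked for a mixed model with 13 participants, 26 sides and 65 papillae.
- **No jaw claim is planned.** The documents state no jaw hypothesis and announce no jaw-specific conclusion. Misreading is a risk in reporting, and labelling the subgroups exploratory would remove much of it.

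The core remains: the stated method cannot answer the only question that a comparison of jaw subgroups raises, and nothing else in the plan does.

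**Conclusion.** The point holds for the HA versus i-PRF comparison. The plan has no test of whether the material difference depends on jaw, so significance in one jaw only is not evidence of jaw dependence.

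Under the assumptions listed in the working, exactly one jaw is significant in about 22–39% of trials at 0.4 SD, 27–50% at 0.6 SD, 21–37% at 0.8 SD, 12–18% at 0.2 SD and 7–10% with no difference. The within-participant contrast stays at about 5%. The logical defect is certain. The rates are ranges, because the documents fix none of effect size, SD, jaw split or correlation.

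The documents do not support a stronger reading: neither that the plan will usually produce a false jaw finding, nor that the within-jaw analyses of change over time share the problem to the same degree. This is a secondary analysis, worth correcting because the correction is cheap.

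**What to change.** Replace the subgroup sentence with:

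> Jaw dependence of the material effect will be assessed by the within-participant difference between the maxillary and mandibular HA minus i-PRF change scores, or by the material-by-jaw term of a mixed model with participant and side effects when participants contribute only one jaw, reported with 95% CI. Jaw-specific estimates are exploratory and descriptive, without separate significance claims. For PPI and other non-normal outcomes the same contrast will be tested with a signed-rank procedure.

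The simple contrast needs one value per participant, jaw and side, so the plan should say how several papillae in one quadrant are combined.

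No new data are needed. The cost is a modest change of framework, since the plan currently contains no mixed model, and that model's behaviour at this sample size should be checked before it is relied on. Power for the contrast is limited (step 6) and falls further if some participants contribute only one jaw. A non-significant result must therefore not be reported as showing that the jaws respond alike; the confidence interval should carry the message.

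### The SAP assigns HA versus i-PRF outcomes to both paired tests and One-Way ANOVA, with no rule on which governs and no unit of analysis for either

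*Combined protocol and SAP*

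**What the plan says.** Under Study design, the trial "included 13 systemically healthy adults with a total of 65 papilla deficiencies in the aesthetic zone", and "one side was randomly assigned HA and the contralateral side i-PRF". Each participant therefore supplies both arms. The Scientific Background gives the reason for this layout when it notes that "previous trials have not used a split-mouth design to minimize interpatient variability".

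The Statistical Analysis Plan then describes the between-material comparison twice.

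- Second paragraph: "Since the study design is split-mouth, inter-group comparisons between HA and i-PRF at each time point" are to be paired, and "comparisons of change scores, will use paired t-tests for normally distributed variables and Wilcoxon signed-rank tests otherwise". The same paragraph reserves non-parametric paired procedures for PPI and paired testing for between-group VAS.
- Third paragraph: a sentence that names both jaw and treatment as groupings covers KTT and IBC-ICP, "as well as intergroup analyses of clinical outcome variables, were performed using the One-Way ANOVA test". It continues that "Post Hoc tests were employed to further investigate significant intergroup differences" where applicable. It exempts no clinical variable, PPI included.

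No sentence says which method is primary, which outcomes each covers, or that one replaces the other. Patients and papilla sites are both mentioned for the normality check, but no unit of analysis is given for the ANOVA or for the paired tests.

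**The concern.** The comparison of the two materials is the trial's central question, and the plan allows two p-values for it without saying which is the result.

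The methods are not interchangeable. One-Way ANOVA treats the two sides of a mouth as independent groups, so differences between participants go back into the error term that the split-mouth layout was meant to clear. If the ANOVA is run on papillae, it also treats several papillae on one randomised side as separately randomised. The first fault makes the test too conservative and the second makes it too liberal. Which one dominates depends on the unit and on variances that the documents do not give.

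The missing unit affects the paired tests as well. Because 65 is odd, the papillae cannot all be matched one-to-one across sides, so choosing the paired tests does not by itself fix the analysis.

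**Working it through.** **Figures to reproduce.** There are none: the documents give no power, effect size, SD or correlation.

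**Inputs from the documents.** 13 participants and 65 papillae (65/13 = 5 on average), with one side per material. The significance levels 0.05 and 0.01 are both named; sidedness is not.

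**Assumptions.** Two-sided 5%; total SD 1; outcome = participant effect + participant-by-side effect + papilla residual, all normal. Variance shares are written (participant, side) = (p, s), and the residual share is e = 1 − p − s. Every participant has a 3/2 split that alternates between materials, giving 7×3 + 6×2 = 33 papillae against 7×2 + 6×3 = 32.

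**Step 1: standard error used by ANOVA on 65 papillae.** The true variance of the difference in means is a·p + b·s + c·e, where

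- a = 7(3/33 − 2/32)² + 6(2/33 − 3/32)² = 0.0122
- b = (7×9 + 6×4)/33² + (7×4 + 6×9)/32² = 87/1089 + 82/1024 = 0.1600
- c = 1/33 + 1/32 = 0.0616

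The ANOVA uses c × E(MSE), with E(MSE) = [65 − (p + s)(87/33 + 82/32) − 2e]/63.

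- At (0.5, 0): the true variance is 0.5×0.0122 + 0.5×0.0616 = 0.0369. The ANOVA uses 0.975×0.0616 = 0.0600. The ratio is 0.61, so the test is conservative.
- At (0, 0.3): the true variance is 0.3×0.1600 + 0.7×0.0616 = 0.0911. The ANOVA uses 0.985×0.0616 = 0.0606. The ratio is 1.50, so the test is liberal.
- At (0.5, 0.2): the true variance is 0.0061 + 0.0320 + 0.0185 = 0.0566. The ANOVA uses 0.9645×0.0616 = 0.0594. The ratio is 0.95, so the two faults nearly cancel.

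**Step 2: ANOVA on 13 versus 13 side means, at (0.5, 0).** The true variance is 0.5(1/3 + 1/2)/13 = 0.0321. The ANOVA uses (2/13)(0.5 + 0.5×5/12) = 0.1090. The ratio is 0.29. With this unit the participant variance can only make the test too conservative.

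**Step 3: simulated type I error.** Each scenario has 40,000 replicates (standard error about 0.1 percentage points near 5%), with all three tests applied to the same data.

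| (p, s) | ANOVA, 65 papillae | ANOVA, 13 v 13 side means |
|---|---|---|
| (0.7, 0) | 0.5% | 0.0% |
| (0.5, 0) | 1.4% | 0.1% |
| (0.3, 0) | 2.7% | 0.9% |
| (0.3, 0.1) | 4.4% | 1.1% |
| (0.5, 0.2) | 4.9% | 0.4% |
| (0.1, 0.2) | 8.0% | 3.3% |
| (0.1, 0.3) | 9.8% | 3.4% |
| (0, 0.3) | 11.0% | 5.1% |

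The paired t-test on 13 side-mean differences stays at 4.9% to 5.1% throughout. If one material always has the 3 papillae (39 versus 26), the papilla ANOVA runs from 0.1% to 10.1%.

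**Step 4: simulated power at a true difference of 0.5 SD, not size-adjusted.**

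| (p, s) | Papilla ANOVA | Side-mean ANOVA | Paired t-test |
|---|---|---|---|
| (0.5, 0) | 53% | 21% | 73% |
| (0.3, 0.1) | 52% | 29% | 51% |
| (0.5, 0.2) | 53% | 19% | 54% |

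With no clustering at all, the papilla ANOVA has about 51% power and the paired test about 44%.

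**The case against.** **The two paragraphs may not conflict.** The ANOVA sentence could concern KTT and IBC-ICP only, but it expressly adds the clinical outcome variables. It could concern jaw-by-treatment groups, which would explain the post hoc tests. That reading is possible, but the text does not state it, it would still contain HA versus i-PRF, and it would still have no participant term. The second paragraph also already gives the jaw subgroups paired or repeated-measures methods.

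**The tenses may settle it.** The second paragraph is in the future tense and the third in the past, so a reader might infer that the ANOVA is what was run. The documents do not say so, and they declare neither precedence nor a deviation.

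**The harm may be small.** At (0.3, 0.1) and (0.5, 0.2) the papilla ANOVA is close to nominal. That stands for those two settings but not for mixed settings generally, as 8.0% at (0.1, 0.2) and 9.8% at (0.1, 0.3) show. It is also tempting to count how often the papilla ANOVA and the paired test fall on opposite sides of 0.05 at 0.5 SD: 16% and 18% of simulated trials in those two settings. This is weak evidence, because the figure is already about 14% with no clustering, where both tests are valid.

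**Lost power may seem to serve the hypothesis.** The Scientific Background expects both materials to work "without clinically meaningful differences between them", so a reader might infer that the ANOVA tilts the trial toward that conclusion. The documents do not support this as a fault of the ANOVA alone: the paired test also has only 44% to 54% power at 0.5 SD in several of these scenarios. Non-significance from either test should not be read as showing no difference, and settling this contradiction does not resolve that.

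**Conclusion.** The contradiction is in the text and depends on no assumption: two methods are given for the same between-material comparison, one of them ignores the pairing, and neither has a unit. This must be fixed.

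The size of the consequence is conditional. Under the assumed shares and the 3/2 split, a nominal 5% test has a type I error of about 0.5% to 11% as a papilla-level ANOVA, about 0% to 5% as a side-mean ANOVA, and about 5% as a paired t-test on side means. The variance shares, papillae per side, normality and two-sided testing are all assumed, and the Wilcoxon and PPI analyses were not simulated.

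A reader might infer that the trial's results are biased in a particular direction. The documents do not support that: they give no correlations and no papilla counts per side, and they do not say which test produced the reported comparison.

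**What to change.** Amend the SAP with a dated change, labelled as made after analysis if that is the case.

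1. For HA versus i-PRF outcome comparisons, replace One-Way ANOVA and its post hoc tests with the second paragraph's paired analysis, and state that this analysis governs.
2. Define the unit as the participant: average the papillae within each side and test the 13 paired differences. A mixed model with participant and participant-by-side random effects is an acceptable alternative.
3. For PPI, use one participant-level summary per side in the non-parametric paired test.
4. Compare KTT and IBC-ICP between treatment sides with the same pairing. A participant random effect for the jaw-versus-jaw comparisons is optional and lies outside this contradiction.
5. State which test was actually run. If it was the ANOVA, disclose that and report the paired result as the between-material result.

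The cost is wording and a re-run in SPSS, with no new data. If there is no within-participant correlation, averaging lowers power at 0.5 SD from about 51% to about 44%. Where clustering within sides is present, p-values may become less favourable.

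### The SAP gives two conflicting rules for testing change over time within a material; on a skewed outcome the verdict can depend on which one is followed

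*Combined protocol and SAP*

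**What the plan says.** All of the relevant text is in the Statistical Analysis Plan section, counted here by paragraph.

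- **Paragraph 1** gives two ways of judging normality. The distribution "was assessed based on skewness and kurtosis values", against a range of ±1.96. In addition, "Normality of continuous data will be assessed using the Shapiro–Wilk test and visual inspection of Q–Q plots".
- **Paragraph 2** covers change from baseline within each material: "repeated-measures ANOVA when assumptions are met, or the Friedman test in the case of non-parametric or ordinal data", with Bonferroni adjustment of the pairwise visit comparisons. It then deals with the papilla index separately: "PPI, being ordinal, will be evaluated with non-parametric paired procedures".
- **Paragraph 3** covers the same comparison: "Intragroup comparisons of variables measured at different time points were conducted using the Repeated Measures ANOVA". It states no condition, no Friedman branch and no exception for PPI.

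Paragraph 2 is in the future tense and paragraph 3 in the past tense. No sentence ranks one above the other. The Study design section sets three visits for the image-based outcomes, which "were measured at baseline, 1 month, and 3 months using ImageJ", in "13 systemically healthy adults with a total of 65 papilla deficiencies in the aesthetic zone".

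**The concern.** The Scientific Background section hypothesises that each material will produce a significant gain in papilla fill, and that the two will not differ by a clinically meaningful amount. The first half of that hypothesis rests on the within-material test over time, and for that test the plan holds two rules.

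Two things are at stake. First, on a right-skewed measure such as BTA the two tests can fall on opposite sides of 0.05. Second, while both rules stand, a reader cannot tell whether the reported test was fixed in advance. The two normality criteria in paragraph 1 widen that freedom.

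This is a separate matter from the between-material tests, where paragraph 3 names One-Way ANOVA and paragraph 2 names paired tests. Settling that conflict would leave this one in place.

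**Working it through.** **Step 1: the two rules side by side.**

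| Outcome type | Paragraph 2 | Paragraph 3 |
|---|---|---|
| Continuous, assumptions hold | Repeated Measures ANOVA | Repeated Measures ANOVA |
| Continuous, assumptions fail | Friedman | Repeated Measures ANOVA |
| Ordinal (PPI) | Friedman / non-parametric paired | Repeated Measures ANOVA |

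The rules agree in the first row only. The third row conflicts whatever the data look like, because PPI is ordinal by definition. The second row conflicts only if an outcome fails its check.

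**Step 2: inputs for the size.** From the documents: k = 3 visits, 13 participants, 65 papillae (65/2 ≈ 32 per material if split evenly, which is an assumption) and the 0.05 level. The plan states no SD, effect size, power or sample-size figure, so there is nothing of its own to reproduce. Distributions, correlations and effects below are assumptions.

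**Step 3: the tests.**
- Repeated Measures ANOVA: F = [n Σ(visit mean − grand mean)²/(k−1)] ÷ [residual sum of squares/((n−1)(k−1))]. With k = 3, the degrees of freedom are 2 and 2 × 12 = 24 at n = 13, and 2 and 2 × 31 = 62 at n = 32.
- Friedman: ranks within each unit across the three visits, referred to chi-square on 2 degrees of freedom.

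**Step 4: both tests on the same simulated data** (2,000 runs per setting, so a Monte Carlo standard error of at most √(0.25/2000) = 1.1 points). Skewed outcome: x = exp[0.8(z + shift)], z with variance 0.7² + 0.714² = 1.00 and between-visit correlation 0.49. The shift is 0, −e/2 and −e at the three visits. The log-SD is therefore 0.8 and the SD of log-change is 0.8 × 0.714 × √2 = 0.81. The median fall at 3 months is 1 − exp(−0.8e): 33% at e = 0.5 and 47% at e = 0.8.

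| n | e | ANOVA p<0.05 | Friedman p<0.05 | Verdicts differ |
|---|---|---|---|---|
| 13 | 0 | 4.1% | 5.1% | 6.2% |
| 13 | 0.5 | 18.6% | 22.5% | 16.9% |
| 13 | 0.8 | 47.2% | 53.1% | 25.7% |
| 32 | 0 | 4.6% | 5.6% | 7.0% |
| 32 | 0.5 | 51.0% | 53.6% | 26.8% |
| 32 | 0.8 | 88.8% | 92.2% | 12.4% |

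The largest power gap here is 53.1 − 47.2 = 5.9 points. Both tests were run on every dataset, whereas paragraph 2 sends only failing datasets to Friedman, so the last column is a ceiling on disagreement between the paragraphs in these settings. The n = 32 rows treat papillae as independent.

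For a four-class ordinal outcome like PPI the verdicts differed in 0.8–3.7% of runs at n = 13 and 1.0–4.9% at n = 32.

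**Step 5: paragraph against paragraph, with Shapiro–Wilk routing.** n = 13, log-normal area, log-SD 0.6–1.0, fall 20–40% by 3 months, SD of log-change 0.3–0.5.
- At 1,500 runs per setting, verdicts differed in 13–28% of trials at a 20% fall, 4–27% at 30% and 0–17% at 40%.
- Some details were then varied: 1-month effect 50–100% of the 3-month effect, correlation of changes 0.5–0.8, and fall defined on the mean or the median. At log-SD 0.6, fall 40%, SD 0.3, disagreement was 0–3% with power of 97–100% under both rules. At log-SD 1.0, fall 40%, SD 0.3 it was 5–12%. At log-SD 1.0, fall 20%, SD 0.5 it was 15–32%.
- Over all runs on this grid the range is roughly 0–34%. Power under paragraph 3 is lower by about 0–27 points, for example 56% against 76% (20 points) and 61% against 85% (24 points).

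**Step 6: is the power gap a like-for-like loss?** Only in part. With log-normal change the median falls more than the mean. With the mean change set to zero, Friedman still rejected in 8–11% of trials. Some of its rejections are therefore not evidence that mean area fell.

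**Step 7: the normality check itself.** In the log-normal data of Step 4, a rule of skewness and kurtosis within ±1.96 and a rule of Shapiro–Wilk p ≥ 0.05 disagreed in about 22–32% of samples. Paragraph 2's own branch is therefore not fixed until one check is named.

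**The case against.** The best defence is that paragraph 3 reports rather than plans. It is in the past tense, as is part of paragraph 1, and it may record the branch taken after the continuous variables passed. Repeated Measures ANOVA is, after all, one of paragraph 2's two options, and the sentence does not say that it covers every variable. For continuous outcomes this reading is possible, though the documents do not confirm it. It cannot cover PPI, which paragraph 2 sends to non-parametric methods because it is ordinal. One could answer that the specific PPI sentence overrides the general one, but the plan does not say so. And for PPI, the one certain contradiction, the tests nearly always agree.

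The inputs are also open to challenge, and this stands. No BTA distribution is given. A log-SD of 1.0 implies a 95% spread of exp(2 × 1.96) ≈ 50-fold, while entry is limited to PPI classes 2 and 3 with class 4 and diastema excluded, which may narrow it. The plan does not say that papillae are averaged to 13 values per material. The routing in Step 5 ignores the ±1.96 criterion.

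A reader might also infer that paragraph 3 inflates false positives by running the ANOVA uncorrected for sphericity. The documents do not support this. Neither paragraph mentions sphericity, and silence does not show that an uncorrected p-value would be used. Inflation to 6.0–8.5% appears only if the two follow-up visits are assumed to correlate 0.9–0.95 with each other and 0.3–0.7 with baseline (about 4–5.4% with Greenhouse–Geisser). With equal correlations on the log scale, the uncorrected ANOVA on skewed data stayed at 4.1–4.6% under no effect.

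**Conclusion.** The contradiction is real and stands in the current text: one within-material question, two rules, no order of precedence. For PPI, paragraph 3 cannot be right under the plan's own rule. The sentence bears directly on the hypothesis that each material improves papilla fill.

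The consequence is a possibility whose size depends on assumptions. For a log-normal area with 13 patient-level values and the ranges in Step 5, verdicts at 0.05 differ in roughly 0–34% of trials, and power under paragraph 3 is lower by about 0–27 points, partly because the two tests address different targets. If the effect is large relative to its variability, both rules give the same answer.

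Three stronger readings go too far. The documents do not show that the verdict on BTA would change, since they give no data on its skewness. They do not show that paragraph 3 always costs substantial power: in some settings the gap is under 1 point. Nor do they show that a test was chosen after seeing results, only that the text does not rule it out.

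**What to change.** - Delete the intragroup sentence in paragraph 3, or state that it applies subject to paragraph 2.
- Name one normality check in paragraph 1. Analyse PPI, and any outcome failing that check, by Friedman with Bonferroni-adjusted signed-rank comparisons between visits.
- If the data are already analysed, list the rule used for each outcome and report the other test as a sensitivity analysis.
- Optionally, report the Greenhouse–Geisser p-value wherever Repeated Measures ANOVA is kept. This is a safeguard, not the repair of a shown error.

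The same edit can bring paragraph 3's between-material sentence into line with paragraph 2. The cost is SAP wording, plus re-running a few tests if analysis is complete. No new data are needed.
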